## Specific Aims

The primary aim of this study is to evaluate the CleanSweep™ Closed Suction System on time to first successful SBT in mechanically ventilated patients in the medical intensive care unit.

Secondary aims of this study are to evaluate the use endotracheal tube sweeping compared to closed suctioning effect on length of mechanical ventilation, length of ICU stay, length of total hospital stay, and occurrence of ventilator-associated events.

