## Introduction

Mechanical ventilation (MV) is utilized when the patient's work of breathing (WOB) exceeds their capacity to do that work, with risk of respiratory muscle failure. Approximately half of the time spent on MV is on the process of weaning and discontinuing this support as soon as possible. The focus on MV liberation is due to the associated complications, including an increased risk of pneumonia. The weaning process can be challenging and is categorized as simple, difficult, or prolonged in regards to weaning success. Difficult to wean patients are categorized as such by failing their initial spontaneous breathing trial (SBT) and require up to three subsequent SBTs to pass; or up to seven days to completely wean from mechanical ventilation after the initial SBT. The difficult and prolonged to wean groups account for approximately 31% of the patients weaned from mechanical ventilation. It has been reported that these groups combined account for a 25% mortality rate. Others reported the incidence and mortality related to these weaning categories in a large cohort study on 257 patients, where the simple to wean group represented 59% with a mortality rate of 13%, the difficult to wean group represented 26% of patients with a 9% mortality rate, and the prolonged weaning group represented 14% of the group with a 32% mortality rate.

Evidence-based guidelines were published over a decade ago to help guide the weaning process and are still applicable today. Once the acute underlying disease process associated with the initiation of mechanical ventilation has improved and spontaneous breathing efforts are evident, patients are assessed for their readiness to wean and extubate. Physiologic signs including respiratory pattern, gas exchange, hemodynamic stability, body temperature, hemoglobin levels, and mental status are all used to determine the discontinuation of mechanical ventilator support. Patients are then assessed for discontinuation of mechanical ventilation by

using a SBT. A SBT involves a low level of mechanical ventilatory support or a T-piece attached to the endotracheal tube. The methods of performing a SBT are variable and the recommendations from the literature are inconsistent on this topic. The main purpose of the SBT is to mimic spontaneous breathing to assess a patient's ability to breathe without the assistance of a mechanical ventilator.

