### **Plans for Data Analysis:**

- **Calculated sample size.** Based on previous institutional data, length of mechanical

ventilation is approximately 6.3 days with a standard deviation of 3.64. Effect is estimated at a 20% reduction in the length of mechanical ventilation ( $6.3 \times .20 = 1.26$  days). Standardized effect size would be 35% ( $1.26/3.64$ ). Setting alpha at 0.05 and power of .80 with standardized effect size of 0.35 would require 136 patients in each group or 272 total number of subjects. Estimated completion would be 18 to 24 months.

- Data for each patient will be recorded in REDCap, a secure web-based database. Descriptive and inferential statistics were calculated from the information collected from patients' charts. Patients were divided into two groups based on randomization. Each group's time to first successful SBT and length of mechanical ventilation outcomes will be compared using an independent T-test if the data is normally distributed. Ventilator-associated conditions and infection related ventilation associated complications rates for both groups will be compared using Chi-Square analysis. Level of significance will be set at  $p < 0.05$ .

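### Length of ventilation, ICU stay and hospital stay have no rule for deaths and mortality is not reported, so a difference in deaths could pass for faster recovery

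*Combined protocol and SAP*

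**What the plan says.** Specific Aims, repeated at the end of the Introduction, gives the secondary aims as the effect of sweeping on "length of mechanical ventilation, length of ICU stay, length of total hospital stay, and occurrence of ventilator-associated events". Mortality is not among them.

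Plans for Data Analysis says that each group's "time to first successful SBT and length of mechanical ventilation outcomes will be compared using an independent T-test", on condition that the data are normally distributed. No alternative test is given, and no method is named for ICU or hospital stay. The data come from patients' charts. Nothing in the document says how a patient who dies is handled: there is no competing-risk analysis, survivors-only rule, ventilator-free-day definition or ranking of death.

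Length of ventilation is also the sizing variable. The sample-size paragraph takes the institutional figure ("ventilation is approximately 6.3 days with a standard deviation of 3.64") and continues: "Effect is estimated at a 20% reduction in the length of mechanical ventilation".

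Mortality appears only as background in the Introduction. It describes a cited cohort of 257 patients grouped by weaning category. Mortality was 13% in the simple group (59% of patients) and 9% in the difficult group (26% of patients). For the third category the text reads: "the prolonged weaning group represented 14% of the group with a 32% mortality rate".

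**The concern.** A duration on the ventilator, in the ICU or in hospital stops when the patient recovers and also when the patient dies. Unless a rule says otherwise, the value read from the chart for someone who dies on day 2 while ventilated is 2 days, which is shorter than that of a survivor weaned on day 6. Patients enter within 24 hours of starting ventilation, so early deaths fall inside the observed period.

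Shorter ventilation and shorter stay are read as benefit. If more patients in one group die early, that group's mean falls for the wrong reason; if fewer die, its mean can rise. Because deaths by group are not a reported outcome, a reader could not separate the two explanations. The Introduction itself says there is little or no data on sweeping and patient outcomes, so a mortality difference in either direction cannot be ruled out in advance.

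This differs from the gap in the primary outcome. A patient who dies before a successful SBT has no value for that outcome, whereas here a value exists and may point the wrong way.

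**Working it through.** **1. The plan's own figure.** Inputs from Plans for Data Analysis: mean 6.3 days, SD 3.64, target 6.3 × 0.20 = 1.26 days, alpha 0.05 (two-sided assumed; the plan does not say) and power 0.80.

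n per group = 2 × (1.96 + 0.84)² × (3.64 / 1.26)² ≈ 2 × 7.85 × 8.35 ≈ 131, or 132 after rounding up. The plan states 136, which is within about 3%. Power at 136 per group is about 0.81. The sizing is reproduced and contains no allowance for deaths.

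**2. Mortality in the cited cohort.** 0.59 × 13 + 0.26 × 9 + 0.14 × 32 = 7.67 + 2.34 + 4.48 = 14.49%, or 14.6% after dividing by 0.99 because the categories sum to 99%. It is used below only as a reference rate for one group.

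**3. Expected shift in mean ventilation.** Assume no device effect on weaning and that a death which truncates ventilation cuts it to 40% of its would-be length. Then:

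shift = (excess mortality) × (share of deaths that truncate) × (1 − 0.40) × 6.3

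- Excess 25% − 14.5% = 10.5 points, all deaths truncate: 0.105 × 1 × 0.60 × 6.3 = 0.40 days.
- Same excess, 31% truncate: 0.105 × 0.31 × 0.60 × 6.3 = 0.12 days.
- Excess 5.5 points (20% against 14.5%), all truncate: 0.055 × 0.60 × 6.3 = 0.21 days.

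The 31% is illustrative: 4.48 / 14.49, the prolonged-weaning share of the cohort's deaths.

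**4. Effect on the test.** Simulation with 136 per group, gamma durations (mean 6.3, SD 3.64), truncation to 40%, no device effect, and a t-test at two-sided 0.05, so 2.5% of trials should favour sweeping by chance. Ranges are over repeat runs.

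| Mortality, sweeping v standard | Share of deaths truncating | Shift (days) | p < 0.05 in favour of sweeping |
|---|---|---|---|
| 14.5% v 14.5% | all | 0.00 | 2.5% to 2.6% |
| 20% v 14.5% | all | −0.20 to −0.21 | 6.5% to 6.8% |
| 20% v 14.5% | 31% | −0.07 | 3.6% |
| 25% v 14.5% | all | −0.39 to −0.40 | 14.0% to 14.8% |
| 25% v 14.5% | 31% | −0.12 | 4.7% to 4.8% |

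**5. Sensitivity to the death-timing assumption.** With lognormal durations of the same mean and SD, and every death truncating either at a uniform fraction of the would-be duration or at an exponential time with mean 2 to 3 days, a 10-point excess gives a shift of 0.31 to 0.45 days, with 10% to 17% of trials falsely favourable.

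**6. How large a chance imbalance could be.** At 14.5% mortality in both groups, the standard error of the difference is √(2 × 0.145 × 0.855 / 136) = 4.3 points. A gap of at least 5 points in either direction has about 24% probability (5 / 4.27 = 1.17 standard errors). A gap of 10.5 points is about 2.5 standard errors.

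No calculation was made for ICU or hospital stay, because the document gives no mean or SD for either.

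**The case against.** The strongest reply is that the plan is silent on deaths, and silence is not a rule. A reader might infer that the plan scores death as a good outcome; it does not say so. Taking the chart duration at face value is the default reading, and that is as far as the text goes. This stands and limits the claim, but silence also leaves the handling of deaths open until the data are seen.

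A reader might also infer that every death is scored in the wrong direction. That is not so. A patient who dies after being weaned has a complete ventilation time, and one who dies after prolonged ventilation has a long, unfavourable one. Only deaths that shorten a duration matter.

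Nor can the 14.5% be taken as this trial's rate. The cohort is grouped by weaning category, and the simple and difficult groups, classed as weaned within defined limits, supply 7.67 + 2.34 = 10.0 of the 14.5 points. The remaining 4.5 come from prolonged weaners, whose ventilation was long. The Introduction does not say when deaths occurred or whether they occurred on the ventilator, and a day-2 death before any SBT fits none of the categories. The share of truncated durations here is unknown and could be lower or higher than 31%.

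Three further points stand:

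- Equal deaths with equal timing cause no bias, and nothing in the document predicts a 10.5-point excess.
- Chance imbalance does not raise the overall error rate. It leaves the affected trial's result hard to interpret.
- The t-test is conditional on normality, which gamma data with this mean and SD would usually fail (skewness 1.16), so the rejection rates are indicative. A rank test on raw durations would still treat an early death as a short value.

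None of this supplies a death rule or a mortality outcome.

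**Conclusion.** The point holds in limited form. The three durations can be ended by death, no rule covers this, and mortality is not reported, so a difference in deaths between groups could not be distinguished from faster recovery.

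The size is unknown. It is zero if deaths and their timing are equal. Under the assumed truncation to 40%, a 10.5-point excess moves mean ventilation by about 0.12 to 0.4 days, which is roughly 10% to 31% of the 1.26-day target (0.12 / 1.26 and 0.40 / 1.26). False favourable results occur in about 5% to 14% of trials instead of 2.5%. The mortality rates, the 40% and the 31% are all assumptions; only the mean, SD and group size come from the plan.

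A reader might conclude that raw length of ventilation should be dropped. The documents do not support that: it is the variable on which 272 was calculated. The point concerns secondary aims, though one of them sizes the trial. It should be corrected, but it does not invalidate the design.

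**What to change.** In Specific Aims (and the matching sentence of the Introduction) and in Plans for Data Analysis:

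1. Add in-hospital mortality by group as a reported outcome.
2. Keep the raw durations, including length of ventilation. Alongside them, prespecify a rank-based comparison for ventilation, ICU stay and hospital stay in which in-hospital death takes the worst rank.
3. Show raw durations separately for survivors and non-survivors, as description only, because those subsets are formed after randomisation.

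The cost is analysis wording and one extra field (in-hospital death) from charts already in use. The sample size need not change, but 272 was not calculated for the composite, and the composite is less directly comparable with the 6.3-day institutional figure. The raw mean preserves that link.

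Ventilator-free days to day 28 is a recognised alternative, but it needs vital status after an earlier discharge. That may not be in the chart, and Special Precautions rules out contacting patients once data collection is complete. Limiting the rule to in-hospital death avoids this.

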## Introduction

Mechanical ventilation (MV) is utilized when the patient's work of breathing (WOB) exceeds their capacity to do that work, with risk of respiratory muscle failure. Approximately half of the time spent on MV is on the process of weaning and discontinuing this support as soon as possible. The focus on MV liberation is due to the associated complications, including an increased risk of pneumonia. The weaning process can be challenging and is categorized as simple, difficult, or prolonged in regards to weaning success. Difficult to wean patients are categorized as such by failing their initial spontaneous breathing trial (SBT) and require up to three subsequent SBTs to pass; or up to seven days to completely wean from mechanical ventilation after the initial SBT. The difficult and prolonged to wean groups account for approximately 31% of the patients weaned from mechanical ventilation. It has been reported that these groups combined account for a 25% mortality rate. Others reported the incidence and mortality related to these weaning categories in a large cohort study on 257 patients, where the simple to wean group represented 59% with a mortality rate of 13%, the difficult to wean group represented 26% of patients with a 9% mortality rate, and the prolonged weaning group represented 14% of the group with a 32% mortality rate.

Evidence-based guidelines were published over a decade ago to help guide the weaning process and are still applicable today. Once the acute underlying disease process associated with the initiation of mechanical ventilation has improved and spontaneous breathing efforts are evident, patients are assessed for their readiness to wean and extubate. Physiologic signs including respiratory pattern, gas exchange, hemodynamic stability, body temperature, hemoglobin levels, and mental status are all used to determine the discontinuation of mechanical ventilator support. Patients are then assessed for discontinuation of mechanical ventilation by

using a SBT. A SBT involves a low level of mechanical ventilatory support or a T-piece attached to the endotracheal tube. The methods of performing a SBT are variable and the recommendations from the literature are inconsistent on this topic. The main purpose of the SBT is to mimic spontaneous breathing to assess a patient's ability to breathe without the assistance of a mechanical ventilator.

A SBT is performed to evaluate a patient's ability to balance the respiratory load with their respiratory capacity. Factors that cause a load/capacity imbalance (e.g., increased  $R_{AW}$ , decreased lung compliance) often result in failed SBTs. Because of this, clinicians should ensure proper conditions when performing SBTs. Mucus buildup in the endotracheal tube, which results in luminal narrowing of the tube, can cause this load/capacity imbalance due to the increase in  $R_{AW}$ . Mietto et al noted that ETT luminal narrowing is common and can increase in airflow resistance. They noted that this narrowing occurred despite adequate humidification and suctioning. Wilson and colleagues studied the pressure drop across a sample of used ETTs and found that 33% of these tubes reflected an inner diameter change that matched an unused tube one size smaller. They also reported that in approximately 20-35% of patients, the change in pressure was greater than 5 cm H2O. Others have reported that endotracheal tube obstruction occurs more often than previously suspected and the onset can be as soon as 24 hours.

We previously studied the impact of ETT scraping on  $R_{AW}$  and found a statistically significant reduction. There is currently little to no data related to the frequency and impact of ETT scraping or sweeping on patient outcomes. However, we now use devices in our facility that have the ability to sweep ETTs; in addition to inline suction catheters (termed *standard* in this document) that cannot sweep ETTs. Thus, the primary aim of this study is to evaluate the CleanSweep™ Closed Suction System, which is used at Rush University Medical Center, on time to first successful SBT in mechanically ventilated patients in the medical intensive care unit. Secondary aims of this study are to evaluate the use endotracheal tube sweeping compared to closed suctioning effect on length of mechanical ventilation, length of ICU stay, length of total hospital stay, and occurrence of ventilator-associated events.

## **Experimental Design and methods**

This is designed as a prospective, randomized control trial, in a large, urban, academic

medical center. This study will include mechanically ventilated patients (n = 272) in the medical intensive care unit (MICU) and adult intensive care unit at Rush University Medical Center. It will exclude patients with a tracheostomy on admission, those requiring extracorporeal membrane oxygenation (ECMO), or transferred from an outside facility receiving more than 24 hours of mechanical ventilation. Two groups will be randomly assigned via computer randomization. The comparison group will be placed on the CleanSweep™ Closed Suction System immediately after intubation or upon arrival to the MICU. ETTs will be cleaned with the balloon sweeping technology every time a respiratory therapist suctioning the patient. The standard group will be placed on the standard in-line suction device. Airway suctioning will be performed in both groups as per department policy (Catheter advanced until resistance is met and withdrawn slowly for a duration no longer than 15 seconds while applying negative pressure). Both groups will also receive a ventilator bundle that consists of head of bed elevation, ETT cuff pressure management, DVT prevention, daily sedation interruption and SBT, and oral care every 4 hours with chlorhexidine at 12pm (noon) and 12am midnight.

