### **Subject Population**

Two hundred and seventy-two orally intubated, adult patients  $\geq 18$  year of age will be enrolled.

Inclusion criteria:

- Age  $\geq 18$  y/o
- Orally intubated with endotracheal tube
- Mechanically ventilated  $< 24$  hours prior to enrollment

Exclusion criteria:

5.15.2020

- Age < 18 y/o
- Tracheostomy tube
- Extracorporeal membrane oxygenation
- Transfer from outside hospital with more than 24 hours of mechanical ventilation

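### Does naming a medical ICU in the aim but two ICUs in the enrolment sentence call for a change to the population or a unit term in the tests?

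*Combined protocol and SAP*

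**What the plan says.** Specific Aims sets the primary question "in mechanically ventilated patients in the medical intensive care unit", and the Introduction repeats it: the device is evaluated "on time to first successful SBT in mechanically ventilated patients in the medical intensive care unit". Experimental Design and methods is wider. It recruits from the "medical intensive care unit (MICU) and adult intensive care unit". The same paragraph has the device fitted "immediately after intubation or upon arrival to the MICU", and the adult ICU is not mentioned again.

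Subject Population describes "Two hundred and seventy-two orally intubated, adult patients" and names no unit. It requires less than 24 hours of ventilation before enrolment and excludes "Transfer from outside hospital with more than 24 hours of mechanical ventilation".

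Allocation is by computer to two groups, with no stratification by unit mentioned. One suction policy applies to both arms, and "Both groups will also receive a ventilator bundle", without distinction by unit. Plans for Data Analysis specifies an independent t-test for time to first successful SBT and length of ventilation if the data are normal, and chi-square for the ventilator-associated event rates. None of these tests has a unit term.

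**The concern.** Read side by side, the aim and the enrolment sentence describe different populations: one unit against two. A reader could not tell from the aim alone whom the primary result describes. The arrival clause adds to the doubt. A patient can be eligible while already intubated, and for one who reaches the adult ICU in that state the text names no start point for the device.

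There is also an analytic worry. If two units contribute patients and differ in typical duration of ventilation, the difference between units adds to the residual variance of an unadjusted test. A trial planned at 80% power might then fall short, and a factor for unit would be a cheap remedy.

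**Working it through.** **Wording.** Four statements bear on the setting.

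- The aim (Specific Aims, repeated in the Introduction) names the medical ICU.
- The enrolment sentence names the MICU and an adult ICU. It is the only sentence that says where the 272 patients come from.
- The arrival clause names the MICU. Its other half, on intubation, is tied to no unit, so it covers a patient intubated in either ICU. The gap is confined to patients who reach the adult ICU already intubated, and the limit of 24 hours of prior ventilation applies to them as to everyone.
- Subject Population names no unit and so contradicts neither reading.

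The likeliest reading is that the aim and the arrival clause are worded more narrowly than the enrolment sentence. Under either reading the eligibility criteria, the allocation and the tests are the same.

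**Inputs for the unit term.** From Plans for Data Analysis: mean 6.3 days, SD 3.64, effect 0.20 × 6.3 = 1.26 days, alpha 0.05 (taken as two-sided), target power 0.80, 136 per arm. Assumed, because the documents give nothing: a between-unit gap D of 1 or 2 days and an adult ICU share p of 50% or 20%.

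**The plan's own figure.** The standardised effect is 1.26/3.64 = 0.346. The two-sample t-test then needs 132 per arm (130 if 0.346 is rounded to 0.35), so the stated 136 is slightly generous. At 136 per arm, noncentral t with 270 df gives power 81.2%.

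**Cost of the term.** With unit in the model there are 269 df, and the variance is multiplied by 1 + 1/269 for chance imbalance. If the units do not differ, power is 81.0%, a loss of 0.14 points.

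**Gain from the term.** The planning SD can be read in two ways.

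- (A) 3.64 is the within-unit SD. The unadjusted test then faces SD = √(3.64² + p(1−p)D²), and the adjusted test faces 3.64.
- (B) 3.64 already pools the units. The unadjusted test keeps 3.64, and the adjusted test faces SD = √(3.64² − p(1−p)D²).

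| p | D (days) | A: total SD | A: power without / with unit | B: within-unit SD | B: power without / with unit | Gain, points |
|---|---|---|---|---|---|---|
| 50% | 1 | 3.674 | 80.5% / 81.0% | 3.605 | 81.2% / 81.8% | 0.6 |
| 20% | 1 | 3.662 | 80.7% / 81.0% | 3.618 | 81.2% / 81.5% | 0.3 |
| 50% | 2 | 3.775 | 78.3% / 81.0% | 3.500 | 81.2% / 84.0% | 2.7 to 2.8 |
| 20% | 2 | 3.727 | 79.3% / 81.0% | 3.551 | 81.2% / 82.9% | 1.7 |

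Gains are taken before rounding and are net of the term's cost.

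**Validity.** In simulations with normal data and an even split between units, type I error was 4.9% to 5.2% with or without the unit term, for gaps of 1, 2 and 3 days. With skewed (gamma) durations it stayed between 4.4% and 5.3% across the t-test and the rank-sum test, each with and without unit. Leaving unit out does not inflate false positives.

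**The case for a change.** The best case for acting is that the contradiction is visible on the page and costs almost nothing to remove. It adds that a 2-day gap under reading (A) takes power to 78.3% or 79.3%, below target, and that one baseline field and one model term would restore 81.0%. A larger gap would strengthen this: with a normal approximation that ignores the term's own cost, an even split and a 3-day gap, the term lifts power from 81.4% to 88.0%. For skewed durations, a unit-stratified rank-sum test gained about 2.3 to 4.3 points at 2 days.

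The inconsistency stands as a matter of wording, and so does the small gap in the arrival clause. The power argument does not carry the same weight. A 2-day gap exceeds the treatment effect itself and is about a third of the 6.3-day mean (2/6.3 = 0.32); a 3-day gap is nearly half (3/6.3 = 0.48). The shortfall also needs 3.64 to be a within-unit SD. The plan introduces it as "Based on previous institutional data", which reads at least as naturally as a pooled figure, and then planned power is untouched. At a 1-day gap the target is met in every row of the table. The shared suction policy and ventilator bundle give no reason to expect a large gap, and no case mix by unit is described.

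**Conclusion.** No change follows. The difference between the aim and the enrolment sentence is a clerical slip. Making the aim, the enrolment sentence and the arrival clause name the same unit or units is an editorial matter. The documents do not settle which wording was intended, and no analysis turns on it. Under individual randomisation at the same ratio in both units, the unadjusted comparisons are unbiased and hold their error rate, and a report can describe the patients by the unit in which they were treated.

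Adjusting for unit is a legitimate option, but omitting it is not a fault. For length of ventilation its effect on power runs from −0.1 to +0.6 points for a gap of 0 to 1 day, and from +1.7 to +2.8 points for 2 days. These figures rest on assumed gaps and shares, and they concern a secondary outcome. The plan gives no SD for time to first successful SBT and no planning rates for the ventilator-associated events, so no gain can be shown for those. The conclusion would weaken only if the institution's own data showed a gap between the units of well over a day.
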